6.2.2.2. Efficacy Analyses

Tabulations (numbers and proportions) per time point will be provided for the categorical parameters (virologic rebounders, responses, FDA snapshot response outcomes) for secondary endpoints at Weeks 24 and 48, respectively. The treatment arms will be compared by 2-sided 95% CIs constructed using Clopper-Pearson method.

Descriptive statistics (n, mean (SD), median, and ranges) per time point will be provided for the continuous parameters, CD4 cell count actual values and the change from baseline in CD4⁺ cell count at Weeks 24 and 48. 95% CIs for the means and mean changes will be calculated.

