The proportion of participants experiencing virologic rebound through Weeks 24 and 48 will be tabulated using descriptive statistics along with the 95% confidence intervals (CIs). The Wilson (Score) method for the CI will be used. The changes from screening/baseline in CD4⁺ cell count at Weeks 24 and 48 will be summarized using descriptive statistics.

The number of identified protease (PR) mutations (including International Acquired Immunodeficiency Virus (AIDS) Society [IAS]-USA primary and secondary PI resistance-associated mutations [RAMs], reverse transcriptase (RT) mutations (including International AIDS Society-United States of America [IAS-USA] nucleoside/nucleotide RT inhibitor [N[t]RTI] RAMs, IAS-USA non-nucleoside RT inhibitor [non-N[t]RTI] RAMs), and integrase (INI) mutations (including International AIDS Society [IAS]-USA INI-RAMs and IAS-USA primary INI mutations), as well as specific mutations associated with resistance to DRV, FTC, and TAF, will be tabulated based on the observed virologic rebound through the study period. Retrospectively, fold change (FC) in 50% effective concentration (EC₅₀) of ARVs may be analyzed and tabulated dependent on the number of virologic rebound and phenotypes available through the study period.

Adherence Analyses: Treatment adherence based on participant self-report, using a 4-day recall will be summarized by means of descriptive statistics and frequency tabulations for both D/C/F/TAF FDC and the INI + TAF/FTC ARV regimen.

Adherence rates will be reported according to the proportion of participants missing 0, 1, 2, 3 or 4 doses using participant self-report 4-day recall at Weeks 4, 12, 24, 36, and 48.

Safety Analyses: For all safety endpoints, descriptive statistics will be used to summarize the endpoints.

The verbatim terms used in the case report form (CRF) by investigators to identify AEs will be categorized according to system organ class and graded according to Division of Acquired Immunodeficiency Syndrome (DAIDS).

Summaries, listings, datasets, or participant narratives may be provided, as appropriate, for those participants who die, who discontinue study intervention due to an AE, or who experience a severe or a SAE.

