9.4.3.2. Resistance/Efficacy Analyses

HIV-1 genotypes, and phenotypes (PhenoSense GT^{\otimes} Plus Integrase) if applicable, will be analyzed from samples of participants with virologic rebound and with HIV-1 RNA \geq 400 copies/mL.

The proportion of virologic suppression (HIV-1 RNA<50 copies/mL) and failure (HIV-1 RNA ≥50 copies/mL) using the FDA snapshot algorithm in the ITT will also be analyzed as a secondary endpoint at Weeks 24 and 48 using descriptive statistics along with 95% confidence interval (CI, Wilson score method).

The proportion of participants experiencing virologic rebound through Week 24 and 48 will be tabulated using descriptive statistics along with the 95% confidence intervals (CI, Wilson score method).

The changes from screening/baseline in CD4⁺ cell count at Weeks 24 and 48 will be summarized using descriptive statistics.

The number of identified protease (PR) mutations (including International AIDS Society [IAS]-USA primary and secondary PI resistance-associated mutations [RAMs], reverse transcriptase (RT) mutations (including IAS-USA nucleoside/nucleotide RT inhibitor [N[t]RTI] RAMs, IAS-USA non-nucleoside RT inhibitor [N[t]RTI] RAMs), and integrase (INI) mutations (including International AIDS Society [IAS]-USA INI-RAMs and IAS-USA primary INI mutations), as well as specific mutations associated with resistance to DRV, FTC, and TAF, will be tabulated based on the observed virologic rebound through the study period. Retrospectively, fold change (FC) in 50% effective concentration (EC₅₀) of ARVs may be analyzed and tabulated dependent on the number of virologic rebounds and phenotypes available through the study period.

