1.1.2. Secondary Objectives

1.1.2.1. Week 24 Objectives

Metabolic:

- To assess changes in body weight when switching to D/C/F/TAF FDC (Immediate Switch Arm) compared to continuing the current INI + TAF/FTC ARV regimen (Delayed Switch Arm)
- To assess changes in body composition when switching to D/C/F/TAF FDC (Immediate Switch Arm) compared to continuing the current INI + TAF/FTC ARV regimen (Delayed Switch Arm)
- To assess change in blood pressure when switching to D/C/F/TAF FDC (Immediate Switch Arm) compared to continuing the current INI + TAF/FTC ARV regimen (Delayed Switch Arm)
- To assess changes in clinical laboratory tests when switching to D/C/F/TAF FDC (Immediate Switch Arm) compared to continuing the current INI + TAF/FTC ARV regimen (Delayed Switch Arm)
- To assess changes in liver biomarkers when switching to D/C/F/TAF FDC (Immediate Switch Arm) compared to continuing the current INI + TAF/FTC ARV regimen (Delayed Switch Arm)
- To assess changes in concomitant medications of interest (including anti- hypertensive, anti-hyperglycemic, and lipid lowering agents) when switching to D/C/F/TAF FDC (Immediate Switch Arm) compared to continuing the current INI + TAF/FTC ARV regimen (Delayed Switch Arm)

Safety:

• To evaluate the safety of switching to D/C/F/TAF FDC (Immediate Switch Arm) compared to continuing the current INI + TAF/FTC ARV regimen (Delayed Switch Arm)

Efficacy:

- To evaluate the virologic outcomes when switching to D/C/F/TAF FDC (Immediate Switch Arm) compared to continuing the current INI + TAF/FTC ARV regimen (Delayed Switch Arm)
- To evaluate immunological changes when switching to D/C/F/TAF FDC (Immediate Switch Arm) compared to continuing the current INI + TAF/FTC ARV regimen (Delayed Switch Arm)

Resistance:

• To assess viral resistance in participants with confirmed HIV-1 RNA rebound for participants switching to D/C/F/TAF FDC (Immediate Switch Arm) compared to continuing the current INI + TAF/FTC ARV regimen (Delayed Switch Arm)

PROs:

- To assess changes in the burden of common symptoms associated with HIV treatment or disease for participants switching to D/C/F/TAF FDC (Immediate Switch Arm) compared to continuing the current INI + TAF/FTC ARV regimen (Delayed Switch Arm)
- To describe responses on the PGIC in participants switching to D/C/F/TAF FDC (Immediate Switch Arm) and in participants continuing the current INI + TAF/FTC ARV regimen (Delayed Switch Arm)

Adherence:

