6.2. Secondary Endpoints and Analysis Methods

6.2.1. Weeks 24 and 48 Endpoints

In the following, the secondary endpoints at Week 24 are defined for D/C/F/TAF FDC regimen (Immediate Switch Arm) versus INI + TAF/FTC ARV regimen (Delayed Switch Arm), while the secondary endpoints at Week 48 are related to D/C/F/TAF FDC (Immediate Switch Arm) only.

Metabolic:

- Change from Baseline in absolute body weight over time
- Proportion of participants with % change from baseline in body weight >5% over time.
- Proportion of participants with % change from baseline in body weight >3% over time.
- Change from Baseline in BMI over time.
- Change from Baseline in body composition as measured by DEXA scan at Week 24 and Week 48, respectively.
- Change from Baseline in waist circumference over time.
- Change in SBP and DBP from Baseline over time.
- Change from Baseline in fasting lipids over time.
- Change from Baseline in fasting glucose over time.
- Change from Baseline in HOMA-IR at Week 24 and Week 48, respectively.
- Change from Baseline in HbA1c at Week 24 and Week 48, respectively.
- Change from Baseline in leptin and adiponectin at Week 24 and Week 48, respectively.
- Change from Baseline in the proportion of participants with advanced fibrosis according to the NAFLD fibrosis score at Week 24 and Week 48, respectively.
- Change from Baseline in the proportion of participants at high risk of NASH according to the HAIR score at Week 24 and Week 48, respectively.
- Proportion of participants having a dose-reduction or complete withdrawal of anti-hypertensive, anti- hyperglycemic, or lipid lowering agents in the Immediate Switch Arm from Baseline to Week 24 and Week 48, respectively or Delayed Switch Arm from Baseline to Week 24.
- Proportion of participants initiating an anti-hypertensive, anti-hyperglycemic, or lipid lowering agent in the Immediate Switch Arm from Baseline to Week 24 and Week 48, respectively or Delayed Switch Arm from Baseline to Week 24.

Safety:

- Incidence of any Grade AEs (related and not related) through Week 24 and Week 48, respectively.
- Incidence of Grade 3 and 4 AEs (related and not related) through Week 24 and Week 48,

- respectively.
- Incidence of discontinuations due to AEs through Week 24 and Week 48, respectively.
- Incidence of SAEs (related and not related) through Week 24 and Week 48, respectively.
- Change from Baseline in clinical laboratory tests over time.
- Incidence of Grade 3 and 4 laboratory abnormalities over time.

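### SAP 6.2.2.2 says the arms will be compared on virologic outcomes by Clopper-Pearson intervals, which cannot give a between-arm contrast and are not the protocol's Wilson intervals

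*SAP*

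**What the plan says.** SAP 6.2.2.2 plans tabulations for "categorical parameters (virologic rebounders, responses, FDA snapshot response outcomes) for secondary endpoints at Weeks 24 and 48, respectively" and then states: "The treatment arms will be compared by 2-sided 95% CIs constructed using Clopper-Pearson method". It names no difference, ratio, test or two-sample interval.

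Protocol 9.4.3.2 covers part of the same ground with another method. Snapshot suppression and failure at the 50-copy threshold are to be analysed "using descriptive statistics along with 95% confidence interval (CI, Wilson score method"), and rebound is to be "tabulated using descriptive statistics along with the 95% confidence intervals (CI, Wilson score method"). For rebound the Protocol synopsis (1.1) agrees: "The Wilson (Score) method for the CI will be used". The protocol names no interval method for the 200-copy outcomes.

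The Week 24 objective in SAP 1.1.2.1 is comparative: "To evaluate the virologic outcomes when switching to D/C/F/TAF FDC (Immediate Switch Arm) compared to continuing the current INI + TAF/FTC ARV regimen (Delayed Switch Arm"). At Week 48 it is not: SAP 6.2.1 says "the secondary endpoints at Week 48 are related to D/C/F/TAF FDC (Immediate Switch Arm) only".

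The SAP does not mention Wilson, and its amendment history records no change of interval method.

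**The concern.** Two things are wrong with one sentence, and they differ in weight.

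- **The named tool does not do the named job.** A Clopper-Pearson interval describes a single binomial proportion. Applied to two arms it yields two intervals, and the comparison is left to the reader's eye. What is lost is a statement of how large a virologic difference between switching and continuing the data allow.
- **The SAP and the protocol disagree on the interval.** The protocol says its SAP will give a more detailed account of the analyses in its statistical section. Here the SAP substitutes another method and gives no reason. With two methods on record, the choice could be made after the data are seen.

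**Working it through.** The plan states no figure that depends on the interval method, so there is none to reproduce. The check asks three things: what each method estimates, how far the two per-arm methods differ, and what a between-arm interval would add.

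**Inputs.** n = 55 per arm (SAP 1.5, Protocol 9.2). z = 1.96 for 95%. The counts are assumed for illustration, because the documents give no expected virologic rates for this trial.

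**Formulas**, for x events in n, with p = x/n:

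- Clopper-Pearson: lower limit = 2.5% quantile of Beta(x, n-x+1); upper limit = 97.5% quantile of Beta(x+1, n-x). The lower limit is 0 if x = 0 and the upper limit is 1 if x = n.
- Wilson: [p + z²/(2n) ± z·√(p(1-p)/n + z²/(4n²))] / (1 + z²/n).
- Newcombe, for d = p1 - p2 with Wilson limits (l1, u1) and (l2, u2): lower = d - √[(p1-l1)² + (u2-p2)²]; upper = d + √[(u1-p1)² + (p2-l2)²].

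The first two take one arm's data only. Only the third is an interval for a contrast.

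**Step 1: Clopper-Pearson against Wilson, per arm, n = 55**

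| x/n | Clopper-Pearson | Wilson | Largest shift in a limit |
|---|---|---|---|
| 2/55 | 0.4 to 12.5% | 1.0 to 12.3% | 0.6 points |
| 49/55 | 77.8 to 95.9% | 78.2 to 94.9% | 1.0 points |
| 52/55 | 84.9 to 98.9% | 85.1 to 98.1% | 0.7 points |
| 55/55 | 93.5 to 100% | 93.5 to 100% | under 0.1 points |

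Over all counts from 45 to 55 responders, the largest shift is 1.1 points (at 45/55). The conflict between the documents is real but numerically small.

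**Step 2: equal arms, 52/55 in each**

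p1 = p2 = 0.9455; Wilson limits 0.8515 and 0.9813.

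- p - l = 0.0940 and u - p = 0.0359 (rounded up from 0.03585).
- Half-width = √(0.0940² + 0.0359²) = 0.1006.
- Difference 0, 95% interval -10.1 to +10.1 points.

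The planned table would show 84.9 to 98.9% twice. It would not state that a deficit of up to about 10 points is compatible with the data.

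**Step 3: unequal arms, 55/55 against 49/55**

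- d = 1.0000 - 0.8909 = 0.1091.
- Wilson limits: 0.9347 to 1.0000, and 0.7817 to 0.9490.
- Lower = 0.1091 - √(0.0653² + 0.0581²) = 0.1091 - 0.0874 = 0.0217.
- Upper = 0.1091 + √(0² + 0.1092²) = 0.1091 + 0.1092 = 0.2183.
- Difference +10.9 points, 95% interval +2.2 to +21.8 points.

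The per-arm Clopper-Pearson intervals, 93.5 to 100% and 77.8 to 95.9%, overlap. Overlap of two one-sample intervals therefore does not answer the comparative question.

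**The case against.** The strongest defence is that nothing inferential hangs on these endpoints. The only hypothesis in either document concerns body weight. The protocol treats virologic outcomes descriptively, with no alpha, margin or non-inferiority claim, and per-arm proportions with intervals satisfy a descriptive plan. Counts will be tabulated, so any reader can compute a difference interval. On this view it would be enough to delete the word "compared". Restoring Wilson would not produce a comparison either, because Wilson is also a one-sample interval.

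Much of this stands, and it sets the size of the point. It does not rescue the sentence: the SAP promises a comparison, the objective asks for one, and the method named cannot deliver it. Deleting the word would make the SAP internally consistent but leave the comparative objective without an estimate.

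Three stronger readings are tempting, and the documents do not support them.

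- **That the plan loses power or distorts the error rate.** A reader might infer a rule that declares a difference when the intervals fail to overlap. The SAP states no such rule, so error rates computed for it would not describe this plan. Nor would a difference interval be a sensitive detector here. At the response rates the protocol cites from an earlier switch study (94.9% and 93.7%), with 55 per arm, exact enumeration shows a Newcombe interval excluding zero in only about 3.3% of trials. Its value lies in bounding the difference.
- **That the trial must demonstrate preserved virologic control.** It sets no such objective or margin, and Protocol 2.3.2 rests virologic safety on earlier studies.
- **That the binary metabolic endpoints share the fault.** The sentence does not cover them. SAP 6.2.2.1 plans them as descriptive summaries without claiming an interval comparison.

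**Conclusion.** The point holds as a correction to a secondary, descriptive analysis. SAP 6.2.2.2 names a one-sample interval for a between-arm comparison, and no other section supplies the missing contrast. The Week 24 virologic objective therefore has no interval for the difference. With the assumed counts, that omitted interval has a half-width of about 10 points at 55 per arm when both arms respond at 52/55.

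The unexplained departure from Wilson is a genuine inconsistency for 50-copy snapshot outcomes and rebound, but it moves per-arm limits by only about 1 point. The primary analysis and the sample size are unaffected.

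The illustrations rest on assumed counts and on the initial 55 per arm. The classification of the methods as one-sample or two-sample rests on no assumption.

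**What to change.** Replace the sentence in SAP 6.2.2.2 with:

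> Per-arm proportions will be given with Wilson score 95% CIs (Protocol 9.4.3.2). For the randomised comparison at Week 24, the between-arm difference in proportions will be given with a Newcombe (Wilson-based) 95% CI, reported descriptively.

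Apply it to confirmed rebound through Week 24 and to snapshot response and failure at Week 24, at both 50 and 200 copies/mL. Keep Week 48 per arm only: by then the Delayed Switch arm is also planned to be on D/C/F/TAF, and the SAP limits those endpoints to the Immediate Switch arm. If Clopper-Pearson is preferred per arm, record the reason for leaving the protocol's method; the Week 24 difference interval is needed either way.

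The cost is two sentences of SAP text and a standard procedure option. It needs no extra data, visits or participants.

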6.2.2.2.1. Genotype and Phenotype

As all patients are expected to be virologically suppressed at time of study entry, standard resistance testing will not be performed. Historical genotypic testing results will be collected and tabulated if available prior to study entry.

For subjects with confirmed virologic rebound (2 consecutive HIV-1 RNA values ≥200 copies/mL at a scheduled or unscheduled visit) and with a HIV-1 RNA value ≥400 copies/mL, HIV-1 genotypic/phenotypic resistance testing (using PhenoSense GT® Plus Integrase¹) will be performed on the confirmed rebound sample if HIV-1 RNA ≥400 copies/mL or on a following visit with HIV-1 RNA ≥400 copies/mL. Other time points may still be analyzed if deemed necessary. The analysis method is described in Section 6.2.1.

6.2.2.3. Adherence Analyses

Adherence rates will be reported according to the proportion of participants missing 0, 1, 2, 3 or 4 doses using participant self-report 4-day recall at Weeks 4, 12, 24, 36, and 48.

Treatment adherence based on participant self-report using a 4-day recall will be summarized descriptively and frequency tabulations for both D/C/F/TAF FDC and the INI + TAF/FTC ARV regimen. Cumulative treatment adherence through Week 48 will be determined. Additionally, all self-reported adherence will be listed.

6.2.2.4. Exploratory Analyses

Descriptive statistics and frequency tabulations, when available, will be presented for all exploratory endpoints.

In addition, for the Alpha melanocyte stimulating hormone, the association analysis whether increases in concentrations of alpha melanocyte stimulating hormone induce a satiety response will be conducted.

7. SAFETY

7.1. Adverse Events

7.1.1. Definitions

Reported AE parameters and grades are based on the Division of AIDS (DAIDS) Table for Grading the Severity of Adult and Pediatric Adverse Events ("DAIDS AE grading table"). All AEs will be coded using MedDRA version 25.0.

Adverse Drug Reaction (ADR)

ADRs will be presented. A current list of all ADRs is in Attachment 1, and upon further clinical evaluation, additional (grouped) terms might need to be added. The medical assessment of the safety data will be performed according to a pre-specified algorithm (attached to the DPS) and will lead to the final list of ADRs. In case multiple lists are available (US definition), ADRs will be tabulated separately per list.

Events of interest

The events of interest (EOI) groups include a broad list of terms to identify potential cases. The preferred terms belonging to each adverse events of interest (AEOI) group will be coded using MedDRA version 25.0.

Since many of the terms used to identify potential cases are clinically non-specific, only those retrieved cases that upon medical review are specifically suggestive of /compatible with the AEs of special interest will be commented on in the CSR.

AEOI groups used for the safety analyses are listed as follows.

- Severe skin reactions
- Rash
- Hepatotoxicity
- Hyperglycaemia
- Lipid abnormalities
- Coronary artery events
- Renal toxicity
- Bone events due to potential PRT/loss of BMD
- Ocular effects (posterior uveitis)
- Lipodystrophy

Incidence of treatment-emergent adverse events (TEAEs) of interest will be summarized as AE summary tables.

A listing of subjects who died will be provided.

7.1.2. Analysis Methods

All safety analyses will be made on the Safety Population. For all safety endpoints descriptive statistics will be used to summarize the endpoints.

The verbatim terms used in the CRF by investigators to identify adverse events will be coded using the Medical Dictionary for Regulatory Activities (MedDRA). Any AE occurring at or after the initial administration of study drug through the day of last dose plus 7 day is considered to be treatment emergent. If the event occurs on the day of the initial administration of study drug, then the event will be assumed to be treatment emergent. If the event date is recorded as partial or completely missing, then the event will be considered to be treatment emergent unless it is known to be prior to the first administration of study drug based on partial onset date or resolution date. All reported treatment-emergent adverse events will be included in the analysis. For each adverse event, the number and percentage of subjects who experience at least 1 occurrence of the given event will be summarized by treatment group. In addition, comparisons between treatment groups will be provided.

A summary will be provided for the following TEAEs:

- any adverse events,
- serious adverse events,

- deaths due to AE,
- adverse events by toxicity grade (as well as AEs with toxicity grade at least 2 and AEs with toxicity grades 3 or 4),
- AEs at least possibly related to study medication,
- AEs for which the medication was temporarily/permanently stopped,
- serious adverse events that were at least possibly related to the medication.

Incidences of AEs for above mentioned analyses will also be presented by SOC and preferred term. A listing of all AEs will be provided. There will be no formal statistical testing.

Summary of adverse events and incidence tabulations for individual AE will be provided for AEOIs and ADRs.

AIDS defining illness based on WHO clinical staging will be tabulated.

AE listings will be provided for subjects who

- had SAEs
- had AEs leading to discontinuation of study drug.
- had grade 3 or 4 AE
- had each AEOI category?

7.2. Clinical Laboratory Tests

7.2.1. Definitions

All clinical laboratory tests will be displayed for the subjects included in the ITT analysis set. Laboratory parameters of the lab subcategories and calculations are listed in Attachment 2.

Number and percentage of subjects with postbaseline clinically important laboratory values and/or markedly abnormal postbaseline values will be presented by treatment group.

7.2.2. Analysis Methods

Descriptive statistics will be presented for all chemistry, hematology, and urinalysis laboratory tests at scheduled time points. If there are retesting, repeating the same analyze from same collected sample, last or retested results will be used in analysis.

Change from baseline to each scheduled time points will be summarized descriptively for chemistry, hematology, and urinalysis (pH, and specific gravity) tests. A box plot of change from baseline to analysis timepoints will be provided for the following laboratory tests: eGFR, ALT and AST.

Cross-tabulations for the worst toxicity grades through Weeks 24 and 48, respectively, versus reference per laboratory test, and cross-tabulations of the worst toxicity grades at Weeks 24 and 48, respectively, versus reference will also be provided if applicable. Subject listings of abnormal laboratory values will be provided.

Descriptive statistics by Division of AIDS (DAIDS) toxicity grade over time will be presented. Shift summaries from baseline DAIDS toxicity grade to the worst on-treatment toxicity grade will also be presented.

If the DAIDS grading is not available, shift tables will be provided summarizing the shift in laboratory values from baseline to weeks 24 and 48 analysis time points with respect to abnormality criteria (low, normal, high).

